### **2.2.3 Exploratory Outcome Measures**

1. Proportion of participants with at least one severe (grade 3) solicited local or systemic reactogenicity event on days 1-8 after RZV dose 2 in each study group
2. Proportion of participants with at least one severe (grade 3) solicited local reactogenicity event on days 1-8 after RZV dose 2 in each study group
3. Proportion of participants with at least one severe (grade 3) solicited systemic reactogenicity event on days 1-8 after RZV dose 2 in each study group
4. Proportion of participants with serious adverse events and adverse events of clinical interest after RZV dose 2 and clinical description of these events in each study group through the entire study period
5. Proportion of participants with at least one moderate-to-severe (Grade 2-3) solicited local or systemic reactogenicity event on days 1-8 after RZV dose 1 in each study group

6. Proportion of participants with at least one moderate-to-severe (Grade 2-3) solicited local or systemic reactogenicity event on days 1-8 after RZV dose 2 in each study group
7. HAI titers by vaccination group and age group:
  - a. The proportion of subjects achieving seroconversion at day 29 (an HAI titer  $\geq$  1:40 at day 29 if the baseline titer is  $< 1:10$  or a minimum four-fold rise in HAI titer if the baseline titer is  $\geq 1:10$ ) for each influenza strain in the respective season's vaccine
  - b. Proportion of subjects with a seroprotective HAI titer ( $\geq 1:40$ ) pre- and post-immunization at day 29 for each IIV antigen in the respective season's vaccine
  - c. The geometric mean HAI titer (GMT) for each IIV antigen in the respective season's vaccine
  - d. The geometric mean fold rise (GMFR) in HAI titer for each IIV antigen in the respective season's vaccine
8. Change in scores on the EuroQOL 5 dimensions-5 level (EQ-5D-5L) and EuroQOL visual analogue scale (EQ VAS) pre-vaccination and post-vaccination will be compared between the vaccination groups and age groups

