## 6 LABORATORY ANALYSES

### ***6.1 Influenza Hemagglutination Inhibition (HAI) Assay***

Influenza Hemagglutination Inhibition (HAI) Assays will be performed on sera collected, contingent on additional funding. Briefly, reference wild-type, reassortant, or vaccine virus strains representative of the specific viral antigens included in the 2021-2022 and 2022-2023 influenza vaccine will be used to evaluate the relative levels of all four influenza strain-specific antibodies in participant serum samples collected pre- and 28 days post-vaccination. To accomplish these activities all participant samples will be interrogated for influenza antibodies against the strains of interest using the influenza hemagglutination inhibition assay (HAI). This assay is considered the “gold-standard” measure by which to evaluate seroconversion/seroprotection in response to seasonal influenza vaccination. This assay will be performed in accordance with the Duke Regional Biocontainment Laboratory Virology Unit’s fully optimized and approved SOP (RVUSOP004 Influenza HI of Serum Samples). Briefly, test samples will be assayed by HAI as duplicate 2-fold dilution series starting at 1:10. Serum dilutions are then incubated with a concentration of virus verified to possess a known potential for red blood cell (RBC) agglutination. The presence of virus-specific antibodies is visualized via incubation of the virus-serum mixture with a RBC solution; the endpoint titer for a given dilution series is then expressed as the reciprocal of the final dilution in which complete HAI is observed. By convention, seronegative samples are defined as having an endpoint HAI titer < 40 and seropositive samples as having an endpoint titer of  $\geq 1:40$ ; and seroconversion as a 4-fold change in endpoint titer relative to pre-immunization baseline or a change from <10 to  $\geq 1:40$  (28).

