3.3 Exploratory

1. Proportion of participants with at least one severe (grade 3) solicited local or systemic reactogenicity event on days 1-8 after RZV dose 2 in each study group.
2. Proportion of participants with at least one severe (grade 3) solicited local reactogenicity event on days 1-8 after RZV dose 2 in each study group.
3. Proportion of participants with at least one severe (grade 3) solicited systemic reactogenicity event on days 1-8 after RZV dose 2 in each study group.
4. Proportion of participants with serious adverse events and adverse events of clinical interest after RZV dose 2 and clinical description of these events in each study group through the entire study period.
5. Proportion of participants with at least one moderate-to-severe (Grade 2-3) solicited local or systemic reactogenicity event on days 1-8 after RZV dose 1 in each study group.
6. Proportion of participants with at least one moderate-to-severe (Grade 2-3) solicited local or systemic reactogenicity event on days 1-8 after RZV dose 2 in each study group.
7. HAI titers by vaccination group and age group:
 - a. The proportion of subjects achieving seroconversion at day 29 (an HAI titer \geq 1:40 at day 29 if the baseline titer is $< 1:10$ or a minimum four-fold rise in HAI titer if the baseline titer is $\geq 1:10$) for each influenza strain in the respective season's vaccine.
 - b. Proportion of subjects with a seroprotective HAI titer ($\geq 1:40$) pre- and post-immunization at day 29 for each IIV antigen in the respective season's vaccine.
 - c. The geometric mean HAI titer (GMT) at baseline (Day 1) and Day 29 for each IIV antigen in the respective season's vaccine.
 - d. The geometric mean fold rise (GMFR) in HAI titer at Day 29 for each IIV antigen in the respective season's vaccine.
8. Change in scores on the EuroQOL 5 dimensions-5 level (EQ-5D-5L) and EuroQOL visual analogue scale (EQ VAS) pre-vaccination and post-vaccination will be compared between the vaccination groups and age groups.

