6. To compare the proportion of participants with moderate-to-severe (Grade 2-3) solicited local or systemic reactogenicity event on days 1-8 after RZV dose 2 in the RZV and allV4 group vs. RZV dose 2 and HD-IIV4 group.

The proportions of participants with at least one moderate-to-severe (Grade 2-3) solicited local or systemic reactogenicity event on days 1-8 after RZV dose 2 in the mITT Population will be compared between vaccine groups using the same statistical methodology as for Primary Objective 1. A one-sided site-stratified noninferiority test to determine if RZV dose 2 and allIV4 is noninferior to RZV dose 2 and HD-IIV4 with the alpha level set at 0.025 and a 10% noninferiority margin.

This information will also be presented by age-group for the subset of subjects aged 65-69 versus those subjects aged 70 years or older. No formal statistical hypothesis testing (i.e., no p-values) will be performed, only the confidence boundary of the difference will be presented.

7. To compare serum hemagglutination inhibition (HAI) antibody titers after RZV dose 1 and HD-IIV4 with RZV dose 1 and allIV4 for each of the four influenza vaccine strains contained in the respective vaccine for that season in the full study population and by age.

The proportion of subjects achieving seroconversion at day 29 (an HAI titer > 1:40 at day 29 if the baseline titer is < 1:10 or a minimum four-fold rise in HAI titer if the baseline titer is > 1:10) for each influenza strain in the respective season's vaccine in each vaccine group will be presented along with the difference between vaccine groups and a 95% confidence interval of the difference in proportions.

The proportion of subjects with a seroprotective HAI titer ($\geq 1:40$) pre- and post-immunization at day 29 for each IIV antigen in the respective season's vaccine in each vaccine group will be presented along with a 95% confidence interval, as well as the difference between vaccine groups and a 95% confidence interval of the difference in proportions.

The geometric mean HAI titer (GMT) at Day 1 and Day 29 for each IIV antigen in the respective season's vaccine in each vaccine group will be presented along with a 95% confidence interval, as well as the difference between vaccine groups (on the log₁₀ scale) and a 95% confidence interval of the difference in GMTs for each vaccine group (on the log₁₀ scale).

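### SAP 8.3 prints the seroconversion rule with strict cut-offs where the endpoint definition has inclusive ones, leaving a baseline titer of 1:10 without a rule

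*SAP*

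**What the plan says.** **Analysis text.** SAP 8.3, Exploratory Objective 7, gives two branches. With an undetectable baseline the rule is "an HAI titer > 1:40 at day 29 if the baseline titer is < 1:10 or a minimum four-fold rise". With a detectable baseline it is "four-fold rise in HAI titer if the baseline titer is > 1:10". Both cut-offs are strict.

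**Endpoint definition.** SAP 3.3 has "an HAI titer \geq 1:40 at day 29 if the baseline titer is" below 1:10 for the first branch and "minimum four-fold rise in HAI titer if the baseline titer is $\geq 1:10" for the second. Protocol 2.2.3 and the Protocol Summary give the same inclusive rule.

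**Assay.** Protocol 6.1 describes duplicate two-fold dilution series beginning at 1:10, with the endpoint titer taken from the last dilution showing complete inhibition.

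**Related text.** In the paragraph after the seroconversion rule, SAP 8.3 sets seroprotection at ≥ 1:40, inclusive. The SAP version table records no change to the seroconversion rule.

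**The concern.** The analysis section is the text a programmer would code from, and it disagrees with the endpoint section of the same SAP. With a continuous measurement, > and ≥ would be interchangeable. Here they are not, because both cut-offs fall on values that the assay reports.

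Two groups of participants are affected: those whose baseline is the lowest measurable titer, and those who go from undetectable to exactly 1:40. If the printed rule is followed, the seroconversion proportions, and the between-group differences and confidence intervals built on them, would not describe the stated endpoint. This applies to each of the four strains, overall and by age group.

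**Working it through.** The documents state no figure for seroconversion that could be reproduced, so the check compares the two rules directly and then illustrates the size.

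**1. Inputs.** Reportable titers (Protocol 6.1): <1:10, 1:10, 1:20, 1:40, 1:80 and so on. Taking the grid up to 1:2560 gives 10 readings, hence 10 × 10 = 100 pairs of baseline and Day 29 titer.

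**2. The two rules** (b = baseline, p = Day 29):

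| Baseline | SAP 3.3 / Protocol 2.2.3 | SAP 8.3 as printed |
|---|---|---|
| b < 10 | responder if p ≥ 40 | responder if p > 40 |
| b = 10 | responder if p ≥ 4b = 40 | no branch applies |
| b > 10 | responder if p ≥ 4b | responder if p ≥ 4b |

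**3. Enumeration.** The rules differ in 1 + 10 = 11 of the 100 pairs:

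- <1:10 to exactly 1:40 (1 pair): responder under SAP 3.3, non-responder under SAP 8.3.
- Baseline exactly 1:10 (10 pairs): unclassified under SAP 8.3. Under SAP 3.3 the 7 pairs with Day 29 at 1:40 or above are responders, and the 3 at 1:20 or below are non-responders.

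The other 89 pairs agree. With ≥ restored at both places, all 100 agree and none is unclassified.

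**4. Size, on assumed inputs only.** The documents give no baseline geometric mean titer (GMT), fold rise or standard deviation (SD). Assume log-normal titers, baseline SD 1.5 to 1.8 log2, SD of the rise 1.4 to 1.6 log2, and four scenarios: (baseline GMT, mean fold rise) = (10, 4), (20, 3), (40, 3) and (20, 5). Simulated titers are placed on the dilution series.

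With baseline 1:10 counted as failure, one run of 400,000 pairs per scenario gave:

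| GMT, rise | SAP 3.3 rule | SAP 8.3 rule | Loss (points) |
|---|---|---|---|
| 10, 4-fold | 49.4% | 26.8% | 49.4 − 26.8 = 22.6 |
| 20, 3-fold | 46.1% | 33.2% | 46.1 − 33.2 = 12.9 |
| 40, 3-fold | 49.7% | 42.0% | 49.7 − 42.0 = 7.7 |
| 20, 5-fold | 63.1% | 45.8% | 63.1 − 45.8 = 17.3 |

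Rounding titers down to the dilution series is closer to how Protocol 6.1 reads the endpoint. Over the same scenarios and SD ranges it gave:

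- baseline 1:10 counted as failure: loss of about 10 to 23 points;
- baseline 1:10 excluded as unclassified: loss of about 2 to 17 points, and only 2 to 3 at GMT 40 with a 3-fold rise.

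At baseline GMT 80 the loss with failure counting is about 4 to 5 points for a 3-fold rise.

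**5. In participants.** If a share f of an arm falls in the affected cells for a strain, the number misclassified or unclassified among 190 per arm is 190 × f. For an assumed f of 2% this is 190 × 0.02 = 3.8; for 15% it is 190 × 0.15 = 28.5.

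**The case against.** **It may be an artefact of reading the PDF.** The SAP 8.3 parenthesis nearly repeats SAP 3.3, and only the two ≥ signs have changed. An underlined > that lost its underline would look like this. Against that, the inclusive sign for seroprotection survives in the next paragraph. That shows the sign could be read there, but not that the seroconversion signs were typed the same way. This part stands: the source page has to be checked, and confidence is less than high until it is.

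**The intended rule is plain.** Three places give ≥, the version table shows no intended change, and a programmer who met a baseline of 1:10 would find no rule and probably turn to SAP 3.3. This also stands, and makes a slip the likeliest explanation. It does not help with <1:10 to 1:40, where the printed rule runs without any gap and gives a different answer.

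**The stakes are low.** Seroconversion is one of four parts of an exploratory objective, and the protocol (3.2.1 and 6.1) makes the HAI testing depend on funding. This is correct.

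**Stronger readings that a reader might infer.**

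- *A baseline of 1:10 can never seroconvert.* The text does not say so. It gives no rule, and failing or excluding these participants is a choice that the SAP leaves open.
- *Protocol 6.1 is a third, conflicting definition.* It describes "seroconversion as a 4-fold change in endpoint titer relative to pre-immunization baseline or a change from <10 to" 1:40 or above. One could read this as undirected, or as counting <1:10 to 1:20. The second reading needs <1:10 to be coded as 5, which the documents do not state, and it would make the sentence's own second clause redundant. The passage presents itself as assay convention, and the direction is clear from its context of response to vaccination. No effect size or rewrite is warranted there.

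**Conclusion.** The point holds as an internal contradiction. As printed, SAP 8.3 has a wrong responder threshold for an undetectable baseline and no rule for a baseline of 1:10. The enumeration depends only on the printed signs and the dilution series.

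The size is an illustration. Roughly 2 to 23 percentage points covers baseline GMT 10 to 40 and 3- to 5-fold rises under the assumed SDs and both ways of handling baseline 1:10. It should not be read as an expected bias, since no input comes from the documents.

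The consequence is confined to one component of Exploratory Objective 7. The primary endpoint, the secondary objectives, the sample size and the noninferiority conclusions are unaffected. The conclusion is conditional on the source page of SAP 8.3 showing strict signs.

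**What to change.** First check the source page of SAP 8.3, Exploratory Objective 7, for underlined signs. If they are inclusive there, nothing needs changing.

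If they are strict, replace the rule with the one in SAP 3.3: Day 29 titer ≥ 1:40 if baseline is < 1:10, or at least a four-fold rise if baseline is ≥ 1:10. If seroconversion has already been programmed, confirm which rule the code applied.

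The cost is two symbols in one sentence of the SAP and a line in its version table. No data, procedure or protocol text changes.

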#### 7.1.4 Secondary and Exploratory Objectives

The statistical methodology described above for the Primary Objective will also be applied to all Secondary Objectives 1 and 2 and Exploratory Objectives 1, 2, 3, 5 and 6. For Secondary Objective 3 and Exploratory Objective 4, the proportion of participants with severe adverse events will be presented in a table along with exact 95% confidence intervals. The confidence intervals will be used to make comparisons and interpretations. For Exploratory Objective 7, seroconversion or seroprotection at day 29 will be compared using a Mantel-Haenszel statistic in a stratified analysis by site. HAI titer (GMTs) and the geometric mean fold rise (GMFR) in HAI titer will be compared using a regression model that will control for site or nonparametric testing if normality assumptions are not met.

For Exploratory Objective 8, the EQ-5D-5L responses are converted to a Utility Index that ranges from -0.109 (worst health) to 1.0 (best health) using the US specific value sets ([http://www.euroqol.org/fileadmin/user\\_upload/Documenten/Excel/Crosswalk\\_5L/EQ-5D-5L\\_Crosswalk\\_Value\\_Sets.xls](http://www.euroqol.org/fileadmin/user_upload/Documenten/Excel/Crosswalk_5L/EQ-5D-5L_Crosswalk_Value_Sets.xls)). The EQ VAS has a range of 0 (worst health) to 100 (best health). The changes from baseline will be assessed within vaccine group using a paired t-test for the index values and VAS. If normality assumptions are not met, the testing will be performed with a Wilcoxon signed-rank test. The Mann-Whitney U test (Wilcoxon rank-sum test) will be used to compare the difference scores from baseline between the two vaccine groups for the index values and VAS.

Proportions for all objectives will be presented in tables and the noninferiority comparisons will be presented in graphical displays as well. There will be no adjustment to the alpha level for these comparisons, with all noninferiority comparisons at the one-side alpha 0.025 level with a 10% noninferiority margin. The alpha level will be set at the two-side 0.05 level for Exploratory Objectives 7, 8, and 9.

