The proportions of participants with at least one severe (Grade 3) solicited systemic reactogenicity event on days 1-8 after RZV dose 2 in the mITT Population will be compared between vaccine groups using the same statistical methodology as for Primary Objective 1. A one-sided site-stratified noninferiority test to determine if RZV dose 2 and allV4 is noninferior to RZV dose 2 and HD-IIV4 with the alpha level set at 0.025 and a 10% noninferiority margin.

This information will also be presented by age-group for the subset of subjects aged 65-69 versus those subjects aged 70 years or older. No formal statistical hypothesis testing (i.e., no p-values) will be performed, only the confidence boundary of the difference will be presented.

4. To compare the proportion of participants with at least one serious adverse event or adverse event of clinical interest after RZV dose 2 in the RZV and allV4 group vs. RZV dose 2 and HD-IIV4 group and describe these events through the entire study period.

The proportion and 95% exact binomial confidence interval in the ITT Population of serious adverse events and events of clinical interest through the entire study period will be presented by site, vaccine group, and relatedness. Listings of the serious adverse events will also be presented. Non-overlapping confidence boundaries will be an indication of a statistical difference between the vaccine groups.

5. To compare the proportion of participants with moderate-to-severe (Grade 2-3) solicited local or systemic reactogenicity event on days 1-8 after RZV dose 1 in the RZV and allV4 group vs. RZV dose 1 and HD-IIV4 group.

The proportions of participants with at least one moderate-to-severe (Grade 2-3) solicited local or systemic reactogenicity event on days 1-8 after RZV dose 1 in the mITT Population will be compared between vaccine groups using the same statistical methodology as for Primary Objective 1. A one-sided site-stratified noninferiority test to determine if RZV dose 1 and allV4 is noninferior to RZV dose 1 and HD-IIV4 with the alpha level set at 0.025 and a 10% noninferiority margin.

This information will also be presented by age-group for the subset of subjects aged 65-69 versus those subjects aged 70 years or older. No formal statistical hypothesis testing (i.e., no p-values) will be performed, only the confidence boundary of the difference will be presented.

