The geometric mean fold rise (GMFR) in HAI titer at Day 29 for each IIV antigen in the respective season's vaccine in each vaccine group will be presented along with a 95% confidence interval.

This information will also be prepared by age-group (65-69 years and ≥ 70 years).

8. To describe and compare changes in health-related quality of life after RZV dose 1 and allIV4 with RZV dose 1 and HD-IIV4 in the full study population and by age-group (administered on study Day 60).

EQ-5D and EQ VAS Scale

The EQ-5D is a standardized, generic measure of health status that provides information on health-related quality of life and activities of daily living relevant to older adults: mobility, self-care, usual activities, pain/discomfort and anxiety/depression (<http://www.euroqol.org/>)

(23). In addition, the instrument contains the EQ Visual Analogue Scale (EQ-VAS) which measures the respondent's self-rated health.

The EQ-5D-5L is the new version of the EQ-5D that increases the levels of severity from three to five to significantly increase reliability and sensitivity while maintaining feasibility and reducing ceiling effects. The descriptive system comprises 5 dimensions of mobility, self-care, usual activities, pain/discomfort, anxiety/depression. For each of these dimensions, there are 5 response levels: no problems, slight problems, moderate problems, severe problems, and extreme problems. The respondent is asked to indicate his/her health state by ticking in the box against the most appropriate statement in each of the 5 dimensions. This decision results in a 1-digit number expressing the level selected for that dimension. The digits for 5 dimensions can be combined in a 5-digit number describing the respondent's health state from 11111 as best health and 55555 as worst health. These numbers are converted to a Utility Index that ranges from -0.109 (worst health) to 1.000 (best health) for US specific values. The minimum clinically important difference ranges from 0.05 to 0.1 depending on health conditions being studied. The EQ VAS records the respondent's self-rated health on a 20 cm vertical, visual analogue scale with endpoints labelled 'the best health you can imagine' (100) and 'the worst health you can imagine' (0). The respondent marks an 'X' on the scale number to indicate how their health is 'today.' The minimum clinically important difference on the VAS is 8.

The EQ VAS has a range of 0 (worst health) to 100 (best health).

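### SAP 8.3 (Exploratory Objective 7) reports the HAI fold rise by arm only, although protocol 7.1.4 promises a site-controlled comparison; the Day 29 titer contrast could also use the Day 1 titer at no cost

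*SAP*

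**What the plan says.** **Protocol 7.1.4** sets a between-arm comparison for both titer summaries: "HAI titer (GMTs) and the geometric mean fold rise (GMFR) in HAI titer will be compared using a regression model". Site is the only covariate it names, and a nonparametric test takes over where normality fails. On the significance level it adds: "The alpha level will be set at the two-side 0.05 level for Exploratory Objectives 7, 8, and 9".

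**SAP 8.3, Exploratory Objective 7**, is worded as a comparison and treats its four summaries differently:

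- Seroconversion and seroprotection: proportions by arm, with a between-arm difference and 95% CI.
- GMT: "The geometric mean HAI titer (GMT) at Day 1 and Day 29 for each IIV antigen" is given by arm, with a between-arm difference on the log10 scale and "a 95% confidence interval of the difference in GMTs for each vaccine group". Day 1 and Day 29 are handled separately, and no model or Day 1 covariate is named.
- GMFR: the sentence opens with "The geometric mean fold rise (GMFR) in HAI titer at Day 29 for each IIV antigen", and all it plans is that the value "in each vaccine group will be presented along with a 95% confidence interval". Nothing further follows for GMFR. The age-group sentence after it repeats the same outputs in two age bands.

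**SAP 5.2** asks for stratification by site when applicable. **SAP 6.3** limits the Immunogenicity Population to participants with both a baseline and a Visit 4 blood draw. The **SAP version table** mentions this objective only for specifying sample collection dates.

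**The concern.** Two separate points arise, and they differ in kind.

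1. The protocol promises a between-arm GMFR comparison with a named method and level. The SAP, which should carry that out, gives two separate per-arm intervals. The site rule in SAP 5.2 cannot fill the gap, because there is no planned contrast to stratify. If nothing changes, the study report has no pre-specified estimate of the GMFR ratio.

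2. The Day 29 GMT contrast leaves out the strongest available predictor of the Day 29 titer. Here the SAP does not depart from the protocol, whose regression also names only site. It is an opportunity to narrow an interval using data already in hand.

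At stake is the clarity and precision of an immunogenicity comparison that is exploratory and, under protocol 3.2.1 and 6.1, depends on funding. The primary and secondary conclusions are unaffected.

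**Working it through.** The documents give no computed figure for Exploratory Objective 7, so there is none to reproduce. The first point rests on the texts set out above; the arithmetic sizes the two points.

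**Inputs**

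- Participants per arm per season: protocol 4.3 plans about 110 + 90 = 200 per season. At 1:1 that is 100 per arm, and with the 5% drop-out of protocol 7.1.1, 100 × 0.95 = 95. Applying that drop-out rate to the serology set is an assumption.
- Assumed, because the documents give neither: SD of log2 titer 1.8 at both visits, and Day 1 to Day 29 correlation rho of 0.4, 0.5 or 0.7.

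**Formula.** The 95% CI of a between-arm ratio is the estimate multiplied and divided by 2^(1.96 × s × √(2/95)), with √(2/95) = 0.1451 and:

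- unadjusted Day 29 GMT: s = SD
- GMFR: s = SD × √(2(1 − rho))
- Day 29 adjusted for Day 1: s = SD × √(1 − rho²)

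| CI factor (×/÷) | rho 0.4 | rho 0.5 | rho 0.7 |
|---|---|---|---|
| GMT, unadjusted | 1.43 | 1.43 | 1.43 |
| GMFR | 1.48 | 1.43 | 1.32 |
| Day 29, Day 1-adjusted | 1.38 | 1.36 | 1.29 |
| Log-scale width, adjusted / unadjusted | 0.92 | 0.87 | 0.71 |

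Across SD 1.5 to 2.1, 80 to 95 per arm and these correlations, the GMFR factor runs from 1.26 to 1.64.

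**How much is lost without the GMFR contrast?** Everyone analysed has both samples, so the log GMFR ratio equals the Day 29 difference in log GMT minus the Day 1 difference. The point estimate can therefore be recovered. The arms are independent, so its variance is SE_A² + SE_B², and both standard errors come from the planned per-arm CIs. These are CIs of the fold rise, so they already contain the within-person correlation.

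The rebuilt CI is slightly wider for two reasons:

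- Degrees of freedom. Combining per-arm t-intervals (94 df, 1.9855) instead of using the regression (190 − 3 = 187 df, 1.9727) gives 1.9855/1.9727 = 1.006.
- Site variation left in the residual. With two equal sites and an assumed site difference of 0.5 log2, the added variance is 0.25 × 0.5² = 0.0625. The fold-rise variance is 1.8² × 2(1 − rho) = 3.89, 3.24 or 1.94. The width then grows by a total factor of 1.006 × √(1 + 0.0625/variance) = 1.015, 1.016 or 1.023.

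A simulation under the same assumptions (4,000 trials per setting, site difference 0 or 0.5 log2) agrees. The rebuilt CI was 0.6 to 2.2% wider on average. Power at a true GMFR ratio of 1.5 was 0.53 / 0.59 / 0.81–0.82 rebuilt, against 0.54 / 0.59–0.60 / 0.82–0.83 by regression.

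**How much does the Day 1 titer add in practice?** Titers lie on a 2-fold grid with a floor at 1:10, which weakens the correlation. In a simulation on that grid, with titers below the floor set to 1:5 (16 settings, observed correlation 0.46 to 0.67), adjusted width over unadjusted GMT width was 0.74 to 0.89. Against the narrower of the GMT and GMFR comparisons it was 0.89 to 0.98, a gain of 2 to 11%.

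**The case against.** The strongest reply is that little is lost. The objective is exploratory and its assay depends on funding. Seroconversion, which is itself relative to baseline, is still contrasted between arms. A GMFR ratio and a close CI can be rebuilt from what the SAP already plans. All of that stands, and it keeps the point minor. It does not remove it: the protocol states a comparison, the SAP does not carry it out, and no reason is recorded.

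It is also fair to say that leaving out the Day 1 titer is no departure from the protocol and no source of bias, since randomization protects the unadjusted contrast. That stands too, and is why the second point is offered only as an improvement.

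Two stronger readings are tempting. First, a reader might infer that the two GMFR intervals are to be judged by whether they overlap, which is much stricter than a two-sided 0.05 test and would cost a good deal of power. The documents do not support this. The sentence "Non-overlapping confidence boundaries will be an indication of a statistical difference between the vaccine groups" belongs to Exploratory Objective 4, and nothing extends it to Objective 7. Second, a reader might infer from the seroconversion cut-offs as they read in SAP 8.3 (strictly greater than) that the rule itself changed. SAP 3.3 and protocol 2.2.3 both use greater than or equal to, and the difference is probably a loss in reading the PDF, so no error is claimed.

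**Conclusion.** The point holds as a minor one, in two parts.

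1. There is a genuine protocol–SAP mismatch: the site-controlled GMFR comparison of protocol 7.1.4 is absent from SAP 8.3. This rests on the text alone and needs no assumption. The cost is the missing stated contrast, not a material loss of power.

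2. Adjusting the Day 29 contrast for the Day 1 titer is a free gain in precision. Its size depends on an SD and a correlation that the documents do not give. The formula gives width factors of about 0.92 to 0.71, the simulation on discrete titers gives 0.89 to 0.74, and the gain over the better of the protocol's own two comparisons is only 2 to 11%. The unadjusted analysis remains unbiased.

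**What to change.** In SAP 8.3, Exploratory Objective 7, for each strain and season:

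1. Add the between-arm GMFR ratio with 95% CI from a regression of log10 fold rise on arm and site, keeping the nonparametric fallback of protocol 7.1.4. Name it as the protocol-specified fold-rise comparison. If the comparison was dropped on purpose, say so and give the reason.
2. As a supporting analysis, compare Day 29 log10 titer with a linear model containing arm, log10 Day 1 titer, site and the randomization age group (65–69, 70 or older), and report the GMT ratio with 95% CI. SAP version 2.0 is dated 5/7/2024 and the documents do not say whether titers had been unblinded by then. If they had, label this model post hoc. Item 1 needs no such label, because the protocol already specifies it.

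The cost is two analysis lines and no new data. The adjusted model assumes a roughly linear relation on the log scale. Its ratio need not equal the ratio of the two per-arm GMFRs: under the assumptions above, chance Day 1 imbalance separates them by a typical (1 SD) factor of 2^((1 − rho) × 1.8 × 0.1451) = 1.11, 1.09 or 1.06. That is why the text should say which of the two answers the fold-rise question.
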